**Table 2-1. Stopping Boundaries for Efficacy Analyses**

Efficacy Analysis	Event (%)	One-sided Decision Boundary		
		OS	PFS (After OS boundary is crossed)	ORR (After PFS boundary is crossed)
Interim	191 (66.7%)	0.006	0.016	0.016
Final	286 (100%)	0.023	0.016	0.016

## 2.2. Final Analysis

The final analysis for the primary endpoint will be conducted after approximately 286 OS events have occurred. Once all outstanding data queries have been resolved, the database will be locked, the blind will be broken, and the efficacy analysis of the study will be performed.

At the final analysis, the type I error rate for testing OS will be controlled by the alpha spending function with O'Brien-Fleming type boundaries. The OS event point will be tested at a one-sided alpha level of 0.023 at 286 OS events. The actual significance levels used will be adjusted based on the actual number of overall events that occur. If the OS endpoint is rejected, the PFS endpoint will be tested at a one-sided alpha level of 0.016. If the PFS endpoint is also rejected, the ORR endpoint will be tested at a one-sided alpha level of 0.016. The actual significance levels used will be adjusted based on the actual number of OS events that occur.

## 2.3. Follow-up Analysis

After the final analysis, additional supplemental analyses of efficacy and safety may be performed to satisfy regulatory requirements or to perform long-term efficacy (eg, OS) and follow-up safety assessments.

## 2.4. Changes from Protocol-Specified Analysis

Primary (OS) and secondary (PFS and ORR) efficacy endpoints may be examined in subgroups defined by baseline tumor programmed death ligand 1 (PD-L1) status (positive vs. negative) (Section 3.4). This analysis was not specified in the protocol. It is added prior to the study unblinding for the primary analysis. Coded archival samples will be provided to the CLIA/CAP-accredited testing laboratory. Both the laboratory and pathologist at the testing laboratory will be blinded to treatment and clinical outcome.

### **3. GENERAL CONSIDERATIONS FOR DATA ANALYSIS**

Data will be summarized using descriptive statistics. For categorical variables, the number and percentage of subjects in each category will be presented; for continuous variables, the number of subjects (n), mean, standard deviation (StD) or standard error (SE), median, first quartile (Q1), third quartile (Q3), minimum, and maximum will be presented.

#### **3.1. Analysis Sets**

Analysis sets define the subjects to be included in an analysis. Analysis sets and their definitions are provided in this section. The analysis set will be identified and included as a subtitle of each table, figure, and listing.

For each analysis set, the number and percentage of subjects eligible for inclusion, as well as the number and percentage of subjects who were excluded and the reasons for their exclusion, will be summarized by treatment group.

A listing of reasons for exclusion from analysis sets will be provided by subject.

##### **3.1.1. Intent-to-Treat Analysis Set**

The ITT Analysis Set includes all subjects who were randomized in the study. This is the primary analysis set for efficacy analyses.

##### **3.1.2. Per-protocol Analysis Set**

The per-protocol (PP) analysis set includes subjects in the ITT and excludes those who meet any one of the following criteria:

- No documented diagnosis of histologically confirmed adenocarcinoma of the stomach or GEJ with inoperable, locally advanced or metastatic disease, not amenable to curative therapy
- Received previous chemotherapy for locally advanced or metastatic gastric or GEJ cancer
- ECOG > 1 at screening
- HER2 positive
- Did not receive study treatment
- Compliance with study drug < 75%

The PP analysis set is the secondary analysis for efficacy analysis.

##### **3.1.3. Safety Analysis Set**

The Safety Analysis Set includes all subjects who received at least 1 dose of andecaliximab/placebo. This is the primary analysis set for safety analyses.

### **3.1.4. Pharmacokinetic Analysis Set**

The Pharmacokinetic (PK) Analysis Set will include all randomized subjects who received at least 1 dose of andecaliximab throughout the study or 1 dose of 5-FU or oxaliplatin on Cycle 2 Day 1, and have at least 1 nonmissing postdose concentration value reported by the PK laboratory. This is the primary analysis set for the summary of plasma concentrations of andecaliximab, 5-FU and oxaliplatin.

### **3.1.5. Pharmacokinetic Substudy Analysis Set**

CCI

### **3.1.6. Immunogenicity Analysis Set**

The Immunogenicity Analysis Set will include all randomized subjects who received at least 1 dose of andecaliximab and have at least 1 nonmissing postdose antidrug antibody (ADA) status reported. This is the primary analysis set for all immunogenicity analyses.

## **3.2. Subject Grouping**

For analyses based on the ITT Analysis Set, subjects will be grouped according to the treatment to which they were randomized.

For analyses based on the PP Analysis Set and Safety Analysis Set, subjects will be grouped according to the randomized treatment except when their actual treatment differs from randomized treatment for the entire treatment duration. In this case, subjects will be grouped based on actual treatment received.

For the PK Analysis Set, subjects will be grouped according to the actual treatment they received.

## **3.3. Strata and Covariates**

Subjects will be randomly assigned to treatment groups via the interactive web response system (IWRS) in a 1:1 ratio using a stratified randomization schedule. Stratification will be based on the following variables:

- Geographic regions: Latin America vs All Other Countries
- ECOG status: 0 vs 1
- Tumor site: Gastric vs GEJ

If there are discrepancies in stratification factor values between the IWRS and the clinical database, the baseline values recorded in the clinical database will be used for analyses.

Efficacy endpoints will be evaluated using stratification factors as covariates or stratification variables for analyses, as specified in Section 6.

In the situation where there is insufficient information in a stratum (ie, if there are < 6 subjects or there is no informative event in a stratum by combined treatment arms), pooling of the stratum may be considered with the smallest adjacent stratum for stratified analyses; the smallest stratum is defined as that stratum having the fewest number of subjects or the fewest number of events in case the former is a tie and the adjacent stratum is defined as a stratum having 2 factors of the 3 at the same level and the other factor at an adjacent level.

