## **5. INVESTIGATIONAL MEDICINAL PRODUCTS**

### **5.1. Randomization, Blinding and Treatment Codes**

Randomization to GS-5745 or placebo will be based on a randomization schedule prepared by Gilead and/or a designee before the start of the study. Eligible subjects will be randomized via an interactive web response system (IWRS). As described in Section 8.5.1, randomization will be stratified by ECOG status (0 or 1) at screening, geographic region (Latin America or other participating countries), and primary tumor site (gastric or GEJ).

The IWRS will be used to maintain a central log documenting screening, to implement randomization, to assess current inventories of study drug, to initiate any necessary resupply of study drug, and to document discontinuation of the study drug.

The IWRS will assign kit numbers and provide instructions for dispensing of blinded study drug (GS-5745/placebo). It is anticipated that subjects will usually begin study drug immediately after randomization.

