### **6.2.7. Performance Status**

Performance status will be scored using the ECOG performance status scale index (refer to [Appendix 4](#)), at Screening, Day 1 of each cycle, EOT, EOS and 30-day Safety Follow-up visits. ECOG used to determine eligibility must be the performance status during the screening period. ECOG performance status on Cycle 1 Day 1 may be waived if it was conducted during screening within 4 days of Cycle 1 Day 1.

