### **8.4. Data Handling Conventions**

#### **8.4.1. General Methods**

By-subject listings will be created for important variables from each eCRF module.

Summary tables for continuous variables will contain the following statistics:

N (number in analysis set), n (number with data), mean, standard deviation (std), 95% confidence intervals (CIs) on the mean, median, minimum, and maximum. Summary tables for categorical variables will include: N, n, percentage, and 95% CIs on the percentage. Unless otherwise indicated, 95% CIs for binary variables will be calculated using the binomial distribution (exact method) and will be 2-sided. Data will be described and summarized by relevant treatment arm, analysis set, and time point. As appropriate, changes from baseline to

each subsequent time point will be described and summarized by treatment arm. Similarly, as appropriate, the best change from baseline during the study will also be described and summarized by treatment arm. Graphical techniques (eg, waterfall plots, Kaplan-Meier curves, etc.) may be used when such methods are appropriate and informative.

The baseline value used in each analysis will be the last (most recent) pre-treatment value.

Subjects with discrepancies between the stratification factor values at randomization and the actual values as documented on data review will be categorized in the analyses according to the actual values. In the situation that there is insufficient information in a stratum (ie, if there are < 6 subjects or there are no events in a stratum), that stratum will be pooled with the smallest adjacent stratum for stratified analyses; the smallest stratum is defined as that stratum having the fewest number of subjects or the fewest number of events in case the former is a tie and the adjacent stratum is defined as a stratum having 2 factors of the 3 at the same level. Data from all sites will be pooled for all analyses. Analyses will be based upon the observed data unless methods for handling missing data are specified. If there is a significant degree of non-normality, analyses may be performed on log-transformed data or nonparametric tests may be applied, as appropriate.

Unless otherwise specified, all analyses will be 1-sided at the 0.025 level of significance.

The following censoring conventions will be applied to tumor control endpoints:

- OS: Data from surviving subjects will be censored at the last time that the subject was known to be alive.

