### 3.8. Analysis Visit Windows

#### 3.8.1. Definition of Baseline and Study Day

Baseline for efficacy is defined as the last observation within 42 days on or prior to randomization, unless otherwise specified. In the rare cases where the screening assessments are after the randomization date but prior to the first dose of andecaliximab/placebo, the assessments will be considered as baseline.

Baseline for safety is defined as the last observation within 42 days prior to first dose of andecaliximab/placebo, unless otherwise specified.

Study Day 1 for the efficacy analysis will be defined as the day of randomization.

Study Day 1 for the safety analysis will be defined as the day for the first dose of andecaliximab/placebo.

Other study days will be derived as follows:

- Assessment Date – Study Day 1 + 1 if Assessment Date  $\geq$  Study Day 1
- Assessment Date – Study Day 1 if Assessment Date  $<$  Study Day 1

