#### 6.1.3. Analysis of the Primary Efficacy Endpoint

OS in months will be calculated by  $(\text{date of event/censoring} - \text{date of randomization} + 1) / 30.4375$ .

The analysis of OS will be performed using the Kaplan-Meier method for the ITT analysis set. The OS distribution of the 2 treatment arm will be compared using the log-rank test, stratified by the stratification factors at randomization. Medians, Q1, Q3, the proportion of subjects who are alive at 6, 12, 18, and 24 months from randomization will be provided along with the corresponding 95% CI. Kaplan-Meier curves will be provided by treatment arm.

In addition, the hazard ratio (HR) between the 2 treatment arms and its 95% CI will be estimated using the Cox proportional hazards regression model, adjusted for the stratification factors at randomization. The analysis strategy for the situation where there is insufficient information in a stratum is detailed in Section 3.3.

Follow-up time for OS will be summarized as a continuous variable with descriptive statistics by treatment arm.

- For subjects who discontinued study due to lost to follow-up or withdraw of consent, duration of OS follow-up = Date of last follow up – randomization date +1
- For the remaining subjects (including those who die), duration of OS follow up = Date of analysis cut-off date – randomization date +1

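### Do the SAP's loose reference to baseline ECOG and its optional pooling of sparse strata leave the primary OS test undefined?

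*SAP*

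**What the plan says.** **Which ECOG is used to randomize.** Protocol 5.1: "randomization will be stratified by ECOG status (0 or 1) at screening". Protocol 6.2.7: "ECOG used to determine eligibility must be the performance status during the screening period". The same section repeats ECOG on Cycle 1 Day 1, with a waiver if a screening score lies within 4 days. Protocol Appendix 2 puts Day 1 within 3 days after randomization, and Protocol 5.1 adds: "It is anticipated that subjects will usually begin study drug immediately after randomization".

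**Which value is analysed.** SAP 3.3: where the randomization system and the database disagree, "the baseline values recorded in the clinical database will be used for analyses". SAP 3.8.1: "Baseline for efficacy is defined as the last observation within 42 days on or prior to randomization". Protocol 8.4.1: "The baseline value used in each analysis will be the last (most recent) pre-treatment value". For stratification discrepancies, however, that same protocol section does not use its baseline definition. It uses the true value found on data review.

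**Levels.** The ECOG strata are 0 and 1 only. The per-protocol set (SAP 3.1.2) excludes patients with "ECOG > 1 at screening".

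**Sparse strata.** Both documents use the same trigger: fewer than 6 patients, or no event. Protocol 8.4.1 then requires pooling with the smallest adjacent stratum, while SAP 3.3 only allows it to be considered. SAP 6.1.3: "The analysis strategy for the situation where there is insufficient information in a stratum is detailed in Section 3.3". SAP 2.4, on changes from the protocol, lists only the PD-L1 subgroups.

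**The concern.** The primary OS test is a stratified log-rank test, and it is the gate for PFS and ORR. If the strata can be formed in more than one way, the plan may not yield a single p-value.

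There are three possible openings. A Day 1 ECOG scored on the day of randomization meets the SAP's definition of baseline, so it might replace the screening score that was actually used to randomize. Eligibility limits only the screening score, so a Day 1 score of 2 is possible and would have no stratum. And a mandatory pooling rule has become discretionary, with no stated decision-maker or time, and the change is not declared.

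At stake would be the position of a borderline OS result relative to z = 1.993, and the possibility that someone picks the reading after seeing the data.

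**Working it through.** **1. The plan's own figures reproduce.** Inputs (Protocol 8.10 and 8.11): HR 0.70, 85% power, one-sided 0.025, one efficacy interim at 66.7% information.
- Fixed design: 4(1.960 + 1.036)² / (ln 0.70)² = 4 × 8.98 / 0.1272 ≈ 282.3, so 283 events.
- With O'Brien-Fleming-type spending at t = 2/3, the boundaries are z = 2.509 (p = 0.0060) and z = 1.993 (p = 0.0231). Power at 286 events is 85.0%.

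Nothing in this point alters those numbers.

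**2. What the discrepancy rule covers.** It starts only when one stratification value is held differently in two places. The stratification factor is screening ECOG. A correctly entered screening score followed by a different Day 1 score is two assessments, not a discrepancy. Two other SAP sections agree:
- SAP 4.1 restates the rule for the value that was used to assign the stratum.
- SAP 6.1.3 stratifies the OS test by the factors as they stood at randomization.

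The word baseline in SAP 3.3 is loose, but the natural reading is the screening value as verified in the database.

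**3. A patient with ECOG 2.** Such a patient appears only if all of these hold: a Day 1 score dated on the randomization day, no 4-day waiver, worsening to 2, and the less natural reading of SAP 3.3. Nothing in the documents shows that this occurs.

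Suppose 8 to 12 such patients, at 15% Latin America and 30% GEJ. The largest region-by-site cell would expect 8 × 0.85 × 0.70 = 4.8 to 12 × 0.85 × 0.70 = 7.1 patients. The other three cells would be smaller. Most would meet the fewer-than-6 trigger, and SAP 3.3 defines an adjacent stratum by the adjacent level of the third factor, which for ECOG 2 is ECOG 1.

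**4. How often pooling is triggered.** The shares are assumed: 45% ECOG 0, 430 patients, eight strata, 40,000 draws per mix. The smallest stratum expects 430 × (Latin America share) × (GEJ share) × 0.45.

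| Latin America, GEJ | Expected smallest stratum | Chance that some stratum has fewer than 6 |
|---|---|---|
| 10%, 20% | 3.9 | 94% |
| 10%, 30% | 5.8 | 63% |
| 15%, 30% | 8.7 | 17% |
| 20%, 30% | 11.6 | 3% |

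The trigger can therefore be real, depending on the mix.

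**5. What pooling alone does.** Eight strata, no ECOG 2, HR 0.70, 30% GEJ, 55% ECOG 1, hazard ratio 1.4 for ECOG 1 against 0, 800 simulated trials per mix:

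| Latin America | Mean absolute change in z | Information, unpooled / pooled | Power, unpooled and pooled | Verdict changes |
|---|---|---|---|---|
| 3% | 0.059 | 0.994 | 82.5%, 82.9% | 0.9% |
| 10% | 0.024 | 0.998 | 82.4%, 82.3% | 0.6% |

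Not pooling costs at most 0.006 × 286 ≈ 1.7 events' worth of information.

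**6. What the choice of ECOG value does.** Assume 5% or 10% of patients move between ECOG 0 and 1 by Day 1 and 2% or 3% reach ECOG 2 (15% Latin America, 30% GEJ). Three readings were compared: screening ECOG, baseline ECOG unpooled, and baseline ECOG pooled.
- Rejection at HR 1.0 (4,000 trials per scenario, Monte Carlo SE about 0.0025): 0.0215 to 0.0275 over all readings and scenarios. Within a scenario the readings differ by at most 0.0253 − 0.0238 = 0.0015.
- Power at HR 0.70 (2,000 trials): 0.822 to 0.848. Within a scenario the readings differ by at most 0.834 − 0.823 = 0.011.
- Screening against unpooled baseline strata: the verdict differs in 2.9% to 4.3% of trials at HR 0.70. At 1% movement and 0.2% ECOG 2 it differs in 1.3%, and with neither in none.

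The verdicts that change go in both directions, which is why error and power hardly move.

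**The case for a change.** The strongest point needs no assumption: the protocol mandates pooling, the SAP makes it optional, and the section meant for such changes is silent. The no-event trigger may also apply early. If deaths fall in proportion to stratum size, the chance of an event-free stratum at the 95-death futility look is 64%, 47%, 24% and 11% for the four mixes in the table of step 4. The monitoring committee sees unblinded efficacy data then. If the best of the three readings were picked after the fact, simulated one-sided error would rise by about 0.5 to 0.7 points. At HR 0.79, the critical value, 4.7% to 6.9% of verdicts would depend on the ECOG reading. If ECOG 2 patients were dropped for lack of a stratum, power would fall by 0.4 to 2.6 points.

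The textual mismatch stands. The rest is weaker:
- An event-free stratum adds nothing to the log-rank numerator or variance, and the futility rule is non-binding and spends no alpha.
- No section permits choosing strata after seeing results, and SAP 3.3 already bases the event trigger on the arms combined.
- Dropping randomized patients would contradict the ITT definition in both documents. Every randomized patient also has a 0-or-1 assignment to fall back on.
- Naming screening ECOG would not close every gap. A patient randomized in error with screening ECOG above 1, whom SAP 3.1.2 foresees, would still have no 0-or-1 value in the database.
- The list of OS sensitivity analyses is absent from the public SAP, so an analysis on the randomization-system strata may already be planned.

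**Conclusion.** The concern does not call for a change. One loose word and one inconsistency over pooling are real, but analysts following the plan would reach a sound result: screening ECOG as verified in the database, with sparse strata pooled by the protocol's rule. The alternatives are also valid tests, with the same type I error within simulation error and power within about 1 point. No method offered is demonstrably better than another.

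The one undisputed mismatch, pooling, changes the OS verdict in 0.6% to 0.9% of trials at HR 0.70 with the eight planned strata. Larger figures need assumed ECOG movement before Day 1, assumed ECOG 2 patients and the less natural reading of SAP 3.3. All the sizes rest on assumed patient mixes and prognostic effects. The conclusion that each fixed reading is valid does not, because strata formed from pre-treatment values keep the randomized comparison intact.

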### 3.4. Examination of Subject Subsets

Primary (OS) and secondary (PFS and ORR) efficacy endpoints will be examined in the following subgroups:

- Stratification factors:
  - Geographic regions: Latin America vs All Other Countries
  - ECOG status: 0 vs 1
  - Tumor site: Gastric vs GEJ
- Extent of Disease
  - Locally Advanced
  - Metastatic

Note that CRF did not collect extent of disease directly and this will be derived as follows. Subjects with disease stage III at screening will be considered “locally advanced” and those with disease stage IV will be considered as “metastatic”.
- Measurability at Baseline
  - Measurable
  - Non-measurable
- Baseline tumor PD-L1 status
  - Positive: PD-L1 expression if Combined Positive Score (CPS)  $\geq 1$ , using PD-L1 immunohistochemistry (IHC) 22C3 pharmDx assay per its label.
  - Negative: PD-L1 expression if CPS  $< 1$ , using PD-L1 IHC 22C3 pharmDx assay per its label.

Note that inevaluable samples will be considered as missing and excluded from the subgroup analysis.

- Age group
  - < 65
  - $\geq$  65
- Gender
  - Male
  - Female
- Race
  - White
  - Non-White

Adverse events (AEs) and lab abnormalities will be examined in the following subgroups:

- Age group
  - < 65
  - $\geq$  65
- Gender
  - Male
  - Female
- Race
  - White
  - Non-White

### **3.5. Multiple Comparisons**

A gate keeping approach will be employed to protect the family wise type I error for the study when testing the primary and secondary endpoints. Assuming the efficacy interim and final analyses are conducted when 191 and 286 OS events have occurred, the testing of the efficacy endpoints will be carried out as follows:

- At the efficacy interim analysis, the OS event point will be tested at a one-sided alpha level of 0.006. If the OS endpoint is not rejected, the study will continue to final analysis. If the OS endpoint is rejected, the IDMC could recommend early stop for efficacy. Furthermore, the PFS endpoint will be tested at a one-sided alpha level of 0.016. Only if the PFS endpoint is rejected will the ORR endpoint be tested at a one-sided alpha level of 0.016.

- At the final analysis, the OS event point will be tested at a one-sided alpha level of 0.023. If the OS endpoint is rejected, the PFS endpoint will be tested at a one-sided alpha level of 0.016. If the PFS endpoint is also rejected, the ORR endpoint will be tested at a one-sided alpha level of 0.016.

The actual significance levels used will be adjusted based on the actual number of OS events that occur.

Overall, this testing strategy employs O'Brian-Fleming type boundary for the primary OS endpoint and the Pocock type boundary for the secondary PFS/ORR endpoints. The testing strategy controls the overall one-sided family-wise type I error to be at 0.025, equivalent to two-sided 0.05 by appropriately adjusting for multiplicity in the efficacy interim and final analyses. Detailed statistical justification of the testing strategy can be found in the [Appendix 3](#).

